## **7 Visit schedule and assessments**

### **7.1 Study flow and visit schedule**

Table 7-1 lists all of the assessments and indicates with an “X”, the visits when they are performed. All data obtained from these assessments must be supported in the patient’s source documentation. The table (“Category” column) indicates which assessments produce data to be entered into the clinical database (D) or remain in source documents only (S).

No CRF will be used as a source document.

Screening/baseline evaluations must be performed  $\leq 21$  days before Cycle 1 Day 1, except for baseline radiological evaluations which must be done within 28 days. Assessments required on Cycle 1 Day 1 that are performed as part of the screening evaluations and within 72 hours prior to the first dose of study treatment, do not need to be repeated on Cycle 1 Day 1. Laboratory and radiological assessments performed as part of standard of care prior to signing informed consent may be used if performed within the screening time window.

During the course of the study visits, test and/or procedures should occur on schedule whenever possible. A visit window of  $\pm 7$  days is allowed. If the infusion of LAG525 or its combination with PDR001 is delayed, the assessments will be shifted accordingly. On PK collection days the windows are provided in [Section 7.2.3](#).

Radiological assessments must be performed  $\pm 7$  days of the scheduled date of the assessment.

Visit name	Category	Protocol Section	Screening Phase	Treatment Phase												Follow-up				
			Screening	Cycle 1					Cycle 2		Cycle 3					Subsequent	EoT	Safety Follow-Up g	Disease Progression F/U	
Day of cycle			-21 to -1	1	2	8	11	15	1	15	1	2	8	11	15	1				
Urinalysis	D	7.2.2.5.4	X																	
Thyroid function	D	7.2.2.5.5	X	X					X		X					X	X			
Cytokines (IL-6)	D	7.2.2.5.6	X	In case of a suspected cytokine release syndrome																
Pregnancy test	D	7.2.2.5.7	X						X		X					X	X			
	S	7.2.2.5.7																X g		
Antineoplastic therapies since discontinuation of study treatment	D	7.1.5																X	X	X

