#### **Disease progression follow up period**

Patients who discontinue study treatment for any reason other than death, disease progression per irRC, lost to follow-up, consent withdrawal, start of new cancer therapy or study termination, also should return for tumor evaluation assessments every 8 weeks until 40 weeks, and then 12 weeks until progression of disease per irRC. If patients refuse to return for these visits or are unable to do so, every effort should be made to contact them or a knowledgeable informant by telephone to determine if the patient had disease progression.

Antineoplastic therapies since discontinuation of study drug will be collected during this follow-up period.

[REDACTED]

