2.1.1 General definitions

Study drug and study treatment

For Arm A and C (monotherapy):

Study drug and study treatment both refer to LAG525 and are used interchangeably.

For Arm B (combo therapy):

Study drug refers to the individual compound i.e., LAG525 or PDR001. Study treatment refers to any combination of study drugs.

Date of first/last administration of study drug and study treatment

The date of first (last) administration of study treatment is derived as the first (last) date when a non-zero dose of any component of study treatment was administered and recorded on the Dosage Administration Record (DAR) eCRF. For the sake of simplicity, the date of first (last) administration of study treatment will also be referred as start (last) date of study treatment.

Study day

The study day for all assessments/events will be calculated using the start date of study treatment as reference. For assessments/events occurring on or after the start date of study treatment, study day will be calculated as:

Study day (days) = Event date – Start date of study treatment + 1.

Therefore, the first day of study treatment is study day 1.

For all assessment/events occurring prior to the start of the study treatment, study day will be negative and will be calculated as:

Study day (days) = Event date – Start date of study treatment.

Study day will be displayed in the data listings.

On-treatment assessment/event

An on-treatment assessment/event is defined as any assessment/event obtained in the time interval from the start date of study treatment until the last date of study treatment (i.e., including combination partner) + 30 days inclusive.

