2.6.3.1 Handling of missing values/censoring/discontinuations

Patients in the dose escalation part who are ineligible for the DDS will be excluded from the primary statistical analysis, although their data will be used for all remaining analyses.

Patients in the phase II part who have BOR of Unknown (UNK) or not assessed (NA) will be considered as a treatment failure in the primary analysis of ORR. Patients with individual scans of UNK or NA will be handled according to RECIST 1.1 as per [CLAG525X2101C Amendment 10 Appendix 1].

Other missing data will simply be noted as missing on appropriate tables/listings.

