2.7 Analysis of the secondary variables

2.7.1 Efficacy definitions

Best overall response (BOR)

The BOR is the best response recorded from the start of the treatment until disease progression/recurrence. For RECIST v1.1 and irRC, any assessments taken before the start of any further antineoplastic therapy will be considered in the assessment of BOR in recognition that response to immunotherapy may be delayed. For both RECIST v1.1 and irRC, if any alternative antineoplastic therapy is taken while on study, any subsequent assessments will be excluded from the BOR determination.

Per RECIST v1.1, CR and PR need to be confirmed with at least two determinations of CR or PR respectively at least 4 weeks apart before progression. In order to classify overall response as SD, a patient must have at least one SD assessment (or better) > 6 weeks after start date of study treatment. In order to classify overall response as PD, a patient must have progression < 12 weeks after start date of study treatment.

Per irRC, irCR, irPR and irPD need to be confirmed with at least two determinations of irCR or irPR or irPD, respectively at least 4 weeks apart. In order to classify overall response as irSD, the patient must have at least one SD assessment (or better) > 6 weeks after start date of study treatment.

Overall response rate (ORR) and Disease control rate (DCR)

ORR is the proportion of patients with a best overall response of CR or PR (RECIST v1.1) or of irCR or irPR (irRC). DCR is the proportion of patients with a best overall response of CR, PR, or SD (RECIST v1.1) or of irCR, irPR, or irSD (irRC). For phase I single agent and combination tables, NCRNPD (RECIST v1.1) or iNCRNPD (irRC) are included in the calculation of DCR.

Progression free survival (PFS)

For assessment per RECIST v1.1, PFS is the time from date of start of treatment to the date of event defined as the first documented progression or death due to any cause. If a patient has not

had an event, PFS is censored at the date of last adequate tumor assessment [[CLAG525X2101C Amendment 10 Appendix 14.3](#)].

Duration of response (DOR)

DOR applies only to patients with a BOR of confirmed CR or PR (RECIST v1.1). For assessment per RECIST v1.1, DOR is defined as the time from the date of the first documented response (CR or PR) to the date of first documented progression, or death due to study indication.

Time to response (TTR)

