TTR applies only to patients with a BOR of confirmed CR or PR (RECIST v1.1). For assessment per RECIST v1.1, TTR is the time between date of start of treatment until first documented response (CR or PR).

Use of alternative cancer therapy

For both RECIST v1.1 and irRC, if any alternative cancer therapy is taken other than palliative radiotherapy or biopsy any subsequent assessments will be excluded from the analysis of endpoints based on tumor response assessments.

Date of last contact

If the patient is not known to have died, the date of last contact will be used. All data excluding the biomarker date will be used to find the date of last contact.

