4.2.2 Other imputations

Incomplete date of initial diagnosis of cancer and date of most recent/first recurrence

Missing day is defaulted to the 15th of the month and missing month and day is defaulted to 01-Jan.

Incomplete assessment dates for tumor assessment

All investigation dates (e.g. MRI scan, CT scan) must be completed with day, month and year. If one or more assessment dates are incomplete but other investigation dates are available, and if the overall response at that assessment is CR/PR/SD/UNK, this/these incomplete date(s) are not considered for calculation of the assessment date and assessment date is calculated as the latest of all investigation dates (e.g. MRI scan, CT scan). Otherwise – if overall response is progression – the assessment date is calculated as the earliest date of all investigation dates at that evaluation number. If all measurement dates have no day recorded, the 1st of the month is used. If the month is not completed, for any of the investigations, the respective assessment will be considered to be at the date which is exactly between previous and following assessment. If

previous and following assessment are not available, this assessment will not be used for any calculation.

Applying the cut-off to tumor assessment

For tumor related assessments, if an evaluation has some assessments done prior to cut-off date and others after the cut-off date, then the evaluation is considered post-cut-off date and will be excluded from analysis.

New anti-neoplastic therapy

Start date:

- If Day is missing, then impute to the max (treatment start date, first day of the month).
- If Day and month are missing then impute to the max (treatment start date, Jan 1).
- If Year, Month and Day are missing then impute to treatment start date.

End date:

No imputation.

Prior anti-neoplastic therapy

Start date:

The same rule which is applied to the imputation of AE/concomitant medication start date will be used, except that 'study treatment start date-1' should be used other than 'study treatment start date' when applicable in the imputation.

End date:

Imputed date = min (start date of study treatment, last day of the month), if day is missing;

Imputed date = min (start date of study treatment, 31DEC), if month and day are missing.

If the end date is not missing and the imputed start date is after the end date, use the end date as the imputed start date.

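### An incomplete start date for a new anticancer therapy can be imputed to the first study dose, turning documented responders into ORR failures and removing documented progressions from PFS and DOR

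*SAP*

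**What the plan says.** SAP 4.2.2 (Other imputations, New anti-neoplastic therapy) has three rules for an incomplete start date. If only the day is missing, the date is the later of treatment start and the first of the month. For a year-only date: "If Day and month are missing then impute to the max (treatment start date, Jan 1" (closing bracket omitted). For a wholly absent date: "If Year, Month and Day are missing then impute to treatment start date".

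These dates drive the efficacy endpoints. SAP 2.7.1 says of best overall response (BOR): "if any alternative antineoplastic therapy is taken while on study, any subsequent assessments will be excluded from the BOR determination". It adds, for all response-based endpoints, "any subsequent assessments will be excluded from the analysis of endpoints based on tumor response assessments", exempting palliative radiotherapy and biopsy. SAP 4.3.3 has the same exclusion for irRC.

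A patient with no qualifying assessment has BOR UNK (Protocol 14.1.17). For the primary ORR analysis, SAP 2.6.3.1 then applies: "Patients in the phase II part who have BOR of Unknown (UNK) or not assessed (NA) will be considered as a treatment failure". For PFS and DOR, the default in SAP Table 4-2, situation F, is censoring at the last adequate assessment. If there is none, Protocol 14.1.25 and 14.1.34 use the start of treatment, giving a duration of one day.

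The protocol describes when these therapies are recorded. The visit schedule lists "Antineoplastic therapies since discontinuation of study treatment", and section 7.1.5 says "Antineoplastic therapies since discontinuation of study drug will be collected during this follow-up period".

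**The concern.** The rule takes the earliest date compatible with the recorded part and bounds it below only by the first study dose. For a therapy collected as started after study drug stopped, that bound allows an impossible order of events. A clerical gap on a follow-up page can then delete scans that were all made before the therapy began.

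The primary endpoint can lose a confirmed responder this way. In groups of about 20 to 40 patients judged against a fixed response count, one patient can matter. Documented progressions can also disappear from PFS, and the patient leaves the DOR analysis because only confirmed responders enter it.

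**Working it through.** **Date rule.** Imputed date = max(first dose, first day of the known month or year), or first dose if nothing is known. With an example first dose of 1 Feb 2018:

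| Recorded start | Imputed start |
|---|---|
| nothing | 1 Feb 2018 |
| 2018 | 1 Feb 2018 |
| 2019 | 1 Jan 2019 |
| Sep 2018 | 1 Sep 2018 |

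A month-only date can wrongly drop only scans made earlier in that same month. If that is the month of first dose, no scan is wrongly lost, because the first is at week 8 (Protocol 7.2.1).

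**Two invented patients.** Durations are end − start + 1 (Protocol 14.1.34).

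- Patient A: first dose 12 Feb 2018; PR on 9 Apr (+56 days) and 4 Jun (+112); PD on 30 Jul (+168); new therapy recorded as 2018. True result: confirmed PR, DOR 112 + 1 = 113 days, PFS event at 168 + 1 = day 169. As written: therapy dated 12 Feb 2018, no scans left, BOR UNK, PFS censored at day 1.
- Patient B: first dose 19 Nov 2018; PR on 14 Jan and 11 Mar 2019; PD on 6 May 2019; new therapy recorded as 2019. It is imputed to 1 Jan 2019, before every scan, so the loss is the same.

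**How often a year-only date does this.** Assumptions: PR at day +56, confirmed at +112, PD at +7w for week w, therapy 14 days after PD, first doses even over a 365-day year, and scans on or after the imputed date dropped. Let d = 0,…,364 be the first-dose day. For PD at week 24, therapy starts at d + 182:

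- Dated to first dose if d + 182 ≤ 364: 183/365 = 50.1%.
- All scans lost if also counting d ≥ 309 (first scan after 1 January): (183 + 56)/365 = 65.5%.
- Confirmed PR lost if instead adding d ≥ 253 (confirming scan after 1 January): (183 + 112)/365 = 80.8%. Where only the confirming scan goes, the PR becomes SD.

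| PD at week | Dated to day 1 | All scans lost | Confirmed PR lost |
|---|---|---|---|
| 24 | 50.1% | 65.5% | 80.8% |
| 32 | 34.8% | 50.1% | 65.5% |
| 40 | 19.5% | 34.8% | 50.1% |
| 52 | 0% | 11.8% | 27.1% |
| 64 | 0% | 0% | 4.1% |

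With a 28-day gap to new therapy the last column is 77.0%, 61.6%, 46.3%, 23.3% and 0.3%. These shares apply only to records with a year-only date.

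**One responder lost at the bar.** The prior is Beta(0.25, 1) (SAP 2.6.2), so the posterior for r/40 is Beta(0.25 + r, 41 − r). The plan's own values reproduce (first row of each pair):

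| Group | Responses | Posterior probability |
|---|---|---|
| NSCLC, renal, mesothelioma | 12/40 | P(ORR > 20%) = 92.3% |
| | 11/40 | 85.6% |
| TNBC | 8/40 | P(ORR > 10%) = 96.6% |
| | 7/40 | 91.7% |
| Melanoma | 18/40 | P(ORR > 30%) = 97.2% |
| | 17/40 | 94.3% |

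In each case the observed-ORR criterion is then missed.

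**Effect on the design.** The exact two-stage binomial reproduces the probabilities in Protocol 10.8: 92.8% (NSCLC, renal, mesothelioma; true ORR 40%), 94.2% (TNBC; 30%) and 92.3% (melanoma; 55%). Suppose each responder is independently lost with probability f, leaving the expansion decision unchanged. In that order, the results are 90.9%, 93.0% and 89.5% for f = 2.5%; 88.7%, 91.6% and 85.9% for 5%; and 83.0%, 88.1% and 76.6% for 10%. The documents give no value for f.

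**The case against.** The strongest reply is that nothing shows the problem is frequent. Missing values are queried at site (Protocol 9.4), and a wholly undated record should be rare. The percentages depend on assumed timings, and the threshold figures need a group of 40 sitting exactly at the bar. Amendment 10 reports 235 expansion patients; over ten groups that is about 24 each (235/10 = 23.5), so many groups may not have reached 40. All of this stands: the total size is unknown and the threshold table is an illustration.

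It can also be said that the earliest date is the conservative choice. For ORR the error is indeed only downward. But deleting documented responses can hide a signal in a signal-seeking phase, and day-1 censoring of documented progressions is not conservative for PFS.

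The year-only rule largely matches the SAP's convention for adverse events and concomitant medication (SAP 4.2.1); only wholly missing dates differ, since those are not imputed there. That is true, but those start dates do not remove tumour assessments.

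Some new therapies may precede the last study dose, for example local therapy after progression during a treatment interruption (Protocol 7.1.2). This stands, and a last-dose bound should not apply to them. The CRF pages are not in the documents, so it must be checked that such records can be separated.

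Finally, the PFS consequence depends on option (1) of situation F. It is the default and the SAP selects no other, so the accurate statement is that events can be lost.

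**Conclusion.** The concern holds. As written, the rule can place a post-treatment therapy at the first study dose and so remove every on-study scan. A confirmed responder becomes an ORR failure and, under the default option, PFS is censored at day 1. This follows from the text alone for a wholly missing date and for a year-only date in the year of first dose. A year-only date in a later year can do the same when the first scan falls after 1 January.

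The ORR bias is downward. The direction for PFS and DOR depends on which patients are affected. The aggregate effect cannot be stated, because the number of incomplete dates is unknown; the conditional shares rest on the assumed response, progression and switch times. The rule should be changed because it contradicts the order in which the protocol collects these therapies and a better bound is already available.

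**What to change.** For therapies recorded as started after discontinuation of study drug, replace treatment start in all three rules by the day after the last study-treatment date. SAP 2.1.1 already derives that date: "The date of first (last) administration of study treatment is derived as the first (last) date when a non-zero dose". The imputed date is then the later of that day and the first day of the known month or year, capped at death, last contact or cut-off. If the known month or year ends before the last dose, query the record. Keep the current rule for therapies recorded as taken during study treatment. Report the current rule for all patients as a sensitivity analysis, with the number of dates imputed by type.

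The new bound is still the earliest possible date for these records, so it cannot credit study drug with a response that followed another therapy.

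The cost is one SAP paragraph, one derivation from an existing variable and one sensitivity run, made by amendment before database lock or addendum after it (SAP 1).

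The repair is partial: a scan made after the last dose but before the true therapy start can still be dropped. In Patient A with last dose 16 Jul 2018, the confirmed PR is kept but PFS is censored at day 113 (the 4 Jun scan, 112 + 1). With last dose on or after 30 Jul, which Protocol 7.2.1 allows because treatment may continue past RECIST progression, the event at day 169 is kept too.

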4.3 Definition and derivation rules for irRC

4.3.1 Total measurable disease burden

In irRC target and new measurable lesions are used to evaluate total measurable tumor burden (TMTB). TMTB is the sum of diameters (SOD) of all target and new measurable lesions. Similar to RECIST v1.1 where SOD of the target lesions is used for determination of target lesion response, for irRC TMTB is used for determination of target and new measurable lesion response.

4.3.1.1 Best percentage change from baseline in TMTB

Best percentage change from baseline in TMTB is defined as the percentage change from baseline to the smallest measured post-baseline TMTB occurring at or before the time of confirmed irPD.

4.3.2 Assessment of disease progression

To facilitate analysis, each assessment of progression is categorized as one of three types: pseudo progression, confirmed progression and unconfirmed progression.

4.3.2.1 Pseudo-progression

Patients with a single irPD, followed by an assessment of irSD or better will be considered to have a pseudo-progression (pPD). For the purposes of analysis, pseudo-progressions are not treated as progression events.

4.3.2.2 Confirmed progression

Confirmed progression 1 (type 1, cPD1) is declared if a patient has 2 consecutive tumor assessments at least 4 weeks (28 days) apart both showing disease progression. Assessments with an UNK response or PD assessments < 28 days after initial PD, are discarded.

The first PD is flagged as cPD1 while all subsequent PDs are flagged as xPD1.

The table below shows two hypothetical data scenarios and programming instructions.

Sequence of assessments	Instructions
1 irPD 2 irUNK 3 irPD (Assessment 1 + 30 days)	
 Assessment 3 is ≥ 28 days after Assessment 1 Assessment 3 represents confirmation of irPD at assessment 1 Assessment 1 irPD is flagged cPD1 Assessment 3 irPD is flagged xPD1
1 irSD 2 irPD 3 irPD (Assessment 2 + 20 days) 4 irPD (Assessment 2 + 30 days)	
 Assessment 3 is < 28 days after Assessment 2 Assessment 4 is ≥ 28 days after Assessment 2 Assessment 4 represents confirmation of irPD at assessment 2 Assessment 2 irPD is flagged cPD1 Assessment 3 and 4 irPDs are flagged xPD1

Confirmed progression 2 (type 2, cPD2) is declared if a patient discontinues treatment following a single PD with no subsequent assessments ≥ 28 days later. Assessments with an UNK response or PD assessments < 4 weeks (28 days) after initial PD, are discarded. Discontinuation of treatment is obtained from EOT case report form.

The assessment is flagged as cPD2 and subsequent PDs (<28 days after first PD) are flagged as xPD2.

The table below shows two hypothetical data scenarios and programming instructions.

Sequence of assessments	Instructions
1 irSD 2 irPD - EOT	
 • Patient withdraws after initial progression (Assessment 2) without confirmation • Assessment 2 irPD is flagged as cPD2
1 irPD 2 irPD (Assessment 1 + 20 days) - EOT	
 • Assessment 2 irPD is <28 days after Assessment 1, so does not represent confirmation • However, patient has completed treatment • Assessment 1 irPD is flagged cPD2 • Assessment 2 irPD is flagged xPD2

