2.7.2 Efficacy evaluation

Analysis of efficacy endpoints will be performed separately for the single agent LAG525 arm and for the combo arm using the FAS.

Evaluation of tumor response will be based on investigator assessment according to RECIST v1.1 and irRC [[CLAG525X2101C Amendment 10 Appendix 14.3](#)].

Efficacy endpoints will include ORR, PFS, DOR and DCR as per RECIST V1.1 and per irRC, for phase I and phase II.

For irRC the key difference from RECIST in the assessments of these endpoints is the requirement for confirmation of PD no less than 4 weeks after the criteria for PD are first met. The date of the first of these two assessments is then the date of confirmed progression. For patients who have ended treatment without a valid confirmation assessment, for the purposes of analysis the single assessment of PD will be treated as a confirmed PD. A single assessment of PD followed by a subsequent assessment of SD or better will be considered as a pseudo-progression, and will not be used for analysis. Individual lesion measurements and overall response assessments will be listed by patient and assessment date. Best overall response per RECIST 1.1 and per irRC will be listed and tabulated.

For all efficacy parameters, data will be listed, summarized, or analyzed by treatment group for the phase I part, and by disease group (groups 6 to 10 and 12 to 16) for phase II patients treated at the MTD(s)/ RP2D(s).

BOR and ORR will be summarized by treatment group for all patients treated in the phase I part. The following analyses will be presented by disease group for patients treated in the phase II part.

- BOR will be summarized
- ORR and DCR will be summarized with an accompanying [90%] exact binomial confidence interval (CI)
- For PFS the survival function will be estimated using the Kaplan-Meier (KM) product limit method and displayed graphically. Median duration, with a two-sided [90%] CI, and 25th and 75th percentiles ([Brookmeyer et al 1982](#), [Klein et al 1997](#)) will be presented. KM estimates of survival proportions at specified time points, along with corresponding [90%] CIs (Greenwood's formula, [Kalbfleisch et al 1980](#)) will also be provided.
- For DOR, KM estimates may be provided if at least 10 patients respond in each dosing regimen/indication.

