4.3.2.3 Unconfirmed progression

Patients with a single irPD, and no assessment of irSD or better (assessment with an irUNK response or irPD assessments < 4 weeks after initial irPD, are discarded) continuing treatment at the time of the analysis will be considered as unconfirmed (uPD).

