4.3.4.1 Progression events

PDs flagged as pPD are not included in time to event analyses.

Patients are classified as follows:

0	No event (censored)
1	Confirmed PD (cPD1 or cPD2)
2	Unconfirmed PD (uPD)

For the primary analysis of time to event endpoints, both confirmed and unconfirmed progression will be included as progression events with date of progression being the date of the assessment flagged as cPD1, cPD2 or uPD according to the algorithm defined in [Section 4.3.2](#).

A sensitivity analysis of time to event endpoints may be conducted in which patients with unconfirmed PD are treated as censored, with date of last adequate assessment = visit date for assessment flagged uPD.

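### SAP 4.3.2 gives no flag to a single unconfirmed irPD first seen after treatment has stopped, although SAP 2.7.2 and Protocol 10.5.2 count it as confirmed progression

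*SAP*

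**What the plan says.** **Body rule.** SAP 2.7.2 and Protocol 10.5.2 deal with patients who ended treatment without a valid confirmation scan: "for the purposes of analysis the single assessment of PD will be treated as a confirmed PD". Neither text requires the progression to come before the end of treatment.

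**Algorithm.** SAP 4.3.2 says that "each assessment of progression is categorized as one of three types: pseudo progression, confirmed progression and unconfirmed progression". The conditions are:
- pPD (4.3.2.1): a single irPD with a later irSD or better. It is not an event.
- cPD1 (4.3.2.2): "is declared if a patient has 2 consecutive tumor assessments at least 4 weeks (28 days) apart both showing disease progression".
- cPD2 (4.3.2.2): "is declared if a patient discontinues treatment following a single PD with no subsequent assessments ≥ 28 days later". In both worked examples EOT follows the irPD.
- uPD (4.3.2.3): a single irPD, no later irSD or better, in a patient "continuing treatment at the time of the analysis will be considered as unconfirmed (uPD").

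**Use of the flags.** SAP 4.3.4.1 dates progression, for the primary analysis of irRC time-to-event endpoints, from the assessment "flagged as cPD1, cPD2 or uPD according to the algorithm defined in" Section 4.3.2. SAP 4.3.3 uses the same flags to assign irPD as best response.

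**Scans off treatment.** Protocol 7.1.5 says that patients who stop for reasons other than irRC progression (with listed exceptions) "also should return for tumor evaluation assessments every 8 weeks until 40 weeks", then every 12 weeks until irRC progression.

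**The concern.** The case can arise by design. Protocol 7.1.3 allows treatment to stop for progression by RECIST 1.1 or on clinical judgement, as well as for adverse events and other reasons. Such a patient may have no irRC progression yet and so stays on the scan schedule. The first irPD may then appear off treatment. A confirming scan may never follow: starting new cancer therapy ends follow-up scanning under Protocol 7.1.5, and SAP 2.7.1 and 4.3.3 exclude later assessments.

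For that patient the SAP contains two rules with different results, and nothing in it says which prevails. A program written from 2.7.2 counts an event at the irPD scan. A program written from 4.3.2 and 4.3.4.1 does not, and under 4.3.4.2 censors at the last irCR, irPR or irSD scan, or at treatment start if there was none. The uPD class offers little rescue: SAP 2.1 times the final report to when patients have potentially completed treatment or discontinued, so few or none will still be on treatment.

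**Working it through.** The documents state no expected value, sample size or power for irRC PFS or DOR, so there is no planned figure to reproduce. The check is to apply the rules to cases.

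**1. Classification.** Each sequence was run through SAP 4.3.2 as written, then with the SAP 2.7.2 rule added.

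| Sequence | 4.3.2 as written | With 2.7.2 |
|---|---|---|
| irSD, irPD, EOT | cPD2 | cPD2 |
| irSD, irPD, still on treatment | uPD | uPD |
| irSD, EOT, irPD, irPD 30 days later | cPD1 | cPD1 |
| irSD, EOT, irPD, irSD | pPD, no event | pPD, no event |
| irSD, EOT, single irPD | no flag | confirmed PD at the irPD |
| irSD, EOT, irPD, irPD 20 days later | no flag | confirmed PD at the first irPD |

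The last two rows fail every class: no second PD at least 28 days on, no discontinuation after the PD, no continuing treatment, no later irSD or better. This contradicts the statement in 4.3.2 that every progression assessment falls into one of its types.

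**2. Consequences if 4.3.2 is programmed alone.**
- PFS and DOR: censored at the last adequate scan unless a later event counts. For PFS, a death after exactly one missing assessment is still an event (SAP Table 4-2, situation C1).
- Best response: irPD needs a flagged event within 84 days (SAP 4.3.3). If there is also no irSD or better after day 42, the patient becomes irUNK. irRC ORR and DCR do not change, because irPD and irUNK both count as neither response nor disease control.

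**3. Direction and illustrative size.** Assumptions, none from the documents: exponential PFS with median *m* weeks; a fraction *f* of patients whose only progression is an unflagged off-treatment irPD, unrelated to its timing; no deaths and no other censoring. From the protocol: scans every 8 weeks to week 40.

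Let *r* = 2^(−8/*m*), the probability of passing one 8-week interval, and *q* = 1 − *r*. Affected patients are censored at the previous scan. At each scan the risk set is then 1 − *fq* and the events are (1 − *f*)*q*, per patient at the start of the interval. The Kaplan-Meier factor is *r*/(1 − *fq*), and 24-week PFS is its cube.

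For *m* = 16: *r* = 0.7071 and *q* = 0.2929. With *f* = 0.10, (0.7071/0.9707)³ = 38.7%, against 0.7071³ = 35.4% with no loss.

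| Median (weeks) | *f* = 0 | 5% | 10% | 20% | 30% |
|---|---|---|---|---|---|
| 12 | 25.0% | 26.4% | 28.0% | 31.5% | 35.6% |
| 16 | 35.4% | 37.0% | 38.7% | 42.4% | 46.6% |
| 24 | 50.0% | 51.6% | 53.2% | 56.7% | 60.6% |

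A simulation of 200,000 patients per setting agrees to within 0.2 points. The estimate always moves up. The *f* values are only a scale, not a forecast.

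**The case against.** A reader might infer that these progressions are lost and that irRC PFS and DOR are therefore inflated. The documents do not support that as a statement of fact. SAP 2.7.2 and Protocol 10.5.2 cover exactly this patient and make the irPD an event. The appendix leans the same way: only pseudo-progressions are excluded from the time-to-event analysis, and the second cPD2 example reasons from the patient having completed treatment. On this view, harm requires a programmer to read one phrase literally and ignore the rest.

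Most of this stands, and it makes the bias conditional. It does not remove the conflict. SAP 4.3.4.1 names the 4.3.2 algorithm as the source of event dates, 4.3.2.2 labels its examples as programming instructions, and neither refers to 2.7.2. SAP 4.3.4.2 sends the progression date to a Section 4.2.4.1 that the SAP does not contain.

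A reader might also want a firm figure for the share affected. Assuming that half of off-treatment irPDs go unconfirmed, and that nobody leaves follow-up, gives 5% to 23% of patients. Neither assumption has support:
- Protocol 7.2.1 and Appendix 2 require irPD to be confirmed after at least 4 weeks. With 80% confirmed, the range is 2.0% to 9.2%.
- Protocol 7.1.5 ends scanning at death, new therapy, loss to follow-up or withdrawal of consent. With half unconfirmed and an assumed exit hazard of 0.03 to 0.10 per week, the range is 1.8% to 11.1%.

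These ranges rest on assumptions too, so none should be quoted as the effect.

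**Conclusion.** SAP 4.3.2 contradicts SAP 2.7.2 and Protocol 10.5.2 on one case: a single irPD, unconfirmed at least 28 days later, first seen after treatment has stopped. Off-treatment irPDs confirmed at least 28 days later are already cPD1 and are not affected.

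If 4.3.2 is programmed literally, irRC PFS and DOR are biased upward and a few early irPDs may be reported as irUNK. If 2.7.2 is applied, the bias is zero. The size cannot be fixed from the documents, because they give neither the share of patients affected nor the irRC PFS distribution.

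Severity is minor. The endpoints touched are secondary and descriptive, in a non-randomised study with no key secondary objective, and Kaplan-Meier estimates for DOR are optional. The primary RECIST 1.1 ORR does not depend on these flags. The conflict is still worth removing, because two programs that each follow the SAP could report different irRC PFS, and the error would favour the treatment.

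**What to change.** Reword cPD2 in SAP 4.3.2.2 along these lines: *declared for a single irPD, not followed by irSD or better and with no evaluable assessment at least 28 days later, in a patient who has ended treatment, whether treatment ended before or after that irPD.*

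Add a third example row to the cPD2 table: irSD – EOT – irPD, flagged cPD2 at the date of the irPD. In the same edit, point the progression-date reference in SAP 4.3.4.2 to 4.3.4.1.

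The cost is one sentence, one table row, one cross-reference and a small program change, made through an SAP amendment or addendum. The protocol need not change, since the new wording matches Protocol 10.5.2. The downside is that irRC PFS and DOR may come out slightly shorter than under the literal algorithm.
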